#### **4.4.7. Prior and Concomitant Therapy**

Administration of any medications or non-study vaccines will be documented in the appropriate eCRF. All concomitant medications taken in the 30 days prior to study enrollment through 28 days following last vaccination or early termination, whichever occurs first, will be recorded. All concomitant medications associated with SAEs, MAAEs, NOCMCs, and PIMMCs through the assessment period for these events will be recorded.

All prescription and over-the-counter medications as well as vitamins and supplements will be recorded.

Assessment of eligibility also will include a review of permitted and prohibited medications (per the exclusion criteria).

Use of new medications should prompt evaluation for the presence of an AE or new chronic medical condition.

Medications which may interfere with the evaluation of the investigational product should not be used unless absolutely necessary. Medications or treatments which are prohibited are listed in the exclusion criteria.

#### **4.4.8. Treatment Compliance**

All participants are to receive 3 doses of study product administered in the clinic. Participants will be directly observed at the time of dosing by a member of the clinical research team who is delegated to administer the study product, and administration of study product will be documented in the appropriate eCRF.

### **4.5. Immunogenicity and Safety Variables**

#### **4.5.1 Safety Variables**

Safety was assessed through collection of solicited and unsolicited adverse events (AEs) and clinical safety laboratory evaluations.

##### **Adverse Events**

ICH E6 defines an AE as any untoward medical occurrence in a patient or clinical investigation participant administered a pharmaceutical product, regardless of its causal relationship to the study treatment. FDA defines an AE as any untoward medical occurrence associated with the use of a drug in humans, whether considered drug related.

An AE can therefore be any unfavorable and unintended sign (including an abnormal laboratory finding), symptom, or disease temporally associated with the use of medicinal (investigational) product. The occurrence of an AE may come to the attention of study personnel during study visits and interviews of a study recipient presenting for medical care, or upon review by a study monitor.

All AEs will be captured on the appropriate eCRF. Information to be collected for AEs includes event description, date of onset, and assessment of severity, relationship to study product and alternate etiology (assessed only by those with the training and authority to make a diagnosis and listed on the Form FDA 1572 as an investigator/sub-investigator), date of resolution, seriousness, and outcome. The severity, relatedness, and seriousness of AEs will be determined using the following definitions and guidelines.

The severity of AEs will be assessed by the investigator using a protocol-defined grading system ([Table 5](#), [Table 6](#), and [Table 7](#)). For events not included in the protocol-defined grading system, the following guidelines will be used to quantify severity:

- Mild (Grade 1): Events that are usually transient and may require only minimal or no treatment or therapeutic intervention and generally do not interfere with the participant's usual activities of daily living.
- Moderate (Grade 2): Events that are usually alleviated with additional specific therapeutic intervention. The event interferes with usual activities of daily living, causing discomfort but poses no significant or permanent risk of harm to the research participant.
- Severe (Grade 3): Events interrupt usual activities of daily living, or significantly affects clinical status, or may require intensive therapeutic intervention. Severe events are usually incapacitating.

The assessment of the AE's relationship to study product will be done by the study clinician licensed to make medical diagnoses and listed on the Form FDA 1572 as the site PI or sub-investigator. Whether the AE is related or not, is not a factor in determining what is or is not reported in this trial. If there is any doubt as to whether a clinical observation is an AE, the event should be reported. In a clinical trial, the study product must always be suspect. The relationship to study product will be assessed for AEs using the terms related or not related:

- Related – There is a reasonable possibility that the study product caused the AE. Reasonable possibility means that there is evidence to suggest a causal relationship between the study product and the AE.
- Not Related – There is not a reasonable possibility that the administration of the study product caused the event.

An AE or suspected adverse reaction is considered a Serious Adverse Event (SAE) if, in the view of either the site PI or sponsor, it results in any of the following outcomes:

- death,
- a life-threatening adverse event, *Note: An AE is considered "life-threatening" if, in the view of either the site PI or sponsor, its occurrence places the patient or participant at immediate risk of death. It does not include an AE that, had it occurred in a more severe form, might have caused death.*
- inpatient hospitalization or prolongation of existing hospitalization,
- a persistent or significant incapacity or substantial disruption of the ability to conduct normal life functions,
- a congenital anomaly/birth defect.
- Important medical events that may not result in death, be life-threatening, or require hospitalizations may be considered serious when, based upon appropriate medical judgment they may jeopardize the patient or participant and may require medical or surgical intervention to prevent one of the outcomes

listed in this definition. Examples of such medical events include allergic bronchospasm requiring intensive treatment in an emergency room or at home, blood dyscrasias or convulsions that do not result in inpatient hospitalization, or the development of drug dependency or drug abuse.

A SUSAR is an adverse event reaction that meets all three of the following criteria:

- Serious
- Unexpected
  - Unexpected event means an event unforeseen by the researcher or the participant, in terms of nature, severity, or frequency, and is not listed in the Investigator's Brochure, package insert, and/or summary of product characteristics.
- At least possibly related to the study product.

NOCMCs are defined as any new ICD-10 diagnosis that is applied to the participant during the duration of the study, after receipt of the study agent, that is expected to continue for at least 3 months and requires continued health care intervention.

MAAEs are any unsolicited AE for which a participant received medical attention, defined as hospitalization, an ER visit, or an otherwise unscheduled visit to or from medical personnel.

PIMMCs constitute a group of AEs that includes diseases which are clearly autoimmune in etiology and other inflammatory and/or neurologic disorders which may or may not have autoimmune etiologies. A list of qualifying conditions is in Appendix C of the protocol [v6.0, 08MAY2023].

Any medical condition that is present at the time that the participant is screened will be considered as baseline and not reported as an AE. However, if the severity of any pre-existing medical condition increases, it should be recorded as an AE.

Solicited adverse events are AEs that are common and known or expected to occur following the administration of the study product. Participants will be assessed for solicited AEs prior to and 30 minutes after each vaccine administration prior to the participant leaving the clinic. On the day of vaccination, participants will receive a thermometer and instructions to complete an e-memory aid to record symptoms for 7 days following each vaccination. The participant e-memory aid will be reviewed with the participant at study visits 48 hours and 7 days after each vaccination (Study Visits 02, 03, 06, 07, 10, and 11). Any symptoms still present after the solicited event collection period (Study Days 1-8 for first vaccination, Study Days 29-36 for second vaccination, and Study Days 57-64 for third vaccination) will continue to be followed until resolution or determined to be stable per investigator. Solicited events will be graded using the Toxicity Grading Scales in [Table 5](#); for quantitative measurements of local injection site reactions, the grading scale classifications of "Small", "Medium", and "Large" will be presented as "Mild", "Moderate", and "Severe" respectively for consistency with other AEs.

- Solicited (local injection site) events listed for this protocol include qualitative measurements of pain, tenderness, ecchymosis, erythema, and induration/edema and quantitative measurements of ecchymosis, erythema, and induration/edema.
- Solicited (systemic) events listed in this protocol include fever (elevated oral temperature), feverishness, fatigue, malaise, myalgia, arthralgia, headache, nausea, and vomiting.

Unsolicited adverse events will be collected starting after the first vaccination through 28 Days after the last vaccination. SAEs, MAAEs, NOCMCs, and PIMMCs will be collected starting after the first vaccination through the final study visit.

## Vital Signs

Per the MOP Appendix B, vital signs that meet the protocol-defined toxicity grading scale ([Table 6](#)) and represent a worsening condition from baseline are reported as an unsolicited AE with the exception of temperatures collected from the time of vaccination through 7 days post vaccination for each vaccination which will be reported as solicited AEs.

The last measurement prior to receiving the first vaccination for each parameter will be considered baseline.

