## 9.7. Vital Signs and Physical Evaluations

Vital sign measurements will include systolic blood pressure, diastolic blood pressure, pulse, and oral temperature. Vital signs will be assessed at screening (Day -30 to -2), Day 1, Day 8, Day 29, Day 36, Day 57,

Day 64, Day 85, and Day 113 for all Cohorts. Cohort 1 was enrolled and completed follow-up under protocol v4.0 (25MAY2022) which also required collection of vital signs at Day 3, Day 15, Day 31, Day 43, Day 59, and Day 71; in the later versions of the protocol followed by Cohorts 2 and 3, vital signs were only collected on these days if indicated. The tables and listing described in this section will only include vital signs collected in clinic on the Vital Signs eCRF. Vital Signs will be graded according to the scale in [Table 6](#).

Vital signs will be tabulated by severity, time point, and treatment group for any assessment ([Table 89](#)) and for each assessment ([Table 90](#), [Table 91](#), [Table 92](#), and [Table 93](#)). Summary statistics of vital signs will be presented for each assessment by time point and treatment group ([Table 94](#), [Table 95](#), [Table 96](#), and [Table 97](#)). All vital signs will be listed by participant and time point ([Listing 14](#)).

An abbreviated physical examination will be performed at screening (Day -30 to -2), and targeted physical exams will be performed as indicated at subsequent visits. The following body systems will be assessed in the abbreviated physical exam: general appearance, skin, head and neck, lungs, heart, liver, spleen, extremities, musculoskeletal and lymph nodes; the targeted physical exam will only include the relevant body systems. All abnormal findings will be listed by participant and time point ([Listing 15](#)).

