**Table 6: Vital Signs Grading Scale**

Measurement	Mild (Grade 1)	Moderate (Grade 2)	Severe (Grade 3)
Tachycardia	101 – 115 bpm	116 – 130 bpm	> 130 bpm or ventricular dysrhythmias
Bradycardia	45 – 49 bpm	40 – 44 bpm	< 40 bpm
Systolic Hypertension	141 – 150 mmHg	151 – 160 mmHg	> 160 mmHg
Systolic Hypotension	85 – 89 mmHg	80 – 84 mmHg	< 80 mmHg
Diastolic Hypertension	91 – 95 mmHg	96 – 100 mmHg	> 100 mmHg
Diastolic Hypotension	50 – 54 mmHg	45 – 49 mmHg	< 45 mmHg
Oral Temperature a	38.0°C – 38.4°C 100.4°F – 101.1°F	38.5°C – 38.9°C 101.2°F – 102.0°F	>38.9°C >102.0°F

Note: Vital signs measurements that meet these grading criteria and represent a worsening of condition from baseline are reported as unsolicited adverse events.

a Oral temperatures assessed from the time of vaccination through 7 days post vaccination for each vaccination will be reported as reactogenicity events rather than as unsolicited adverse events.

**12.4.1 Individual Laboratory Measurements and Abnormal Laboratory Values****Table 7: Laboratory Adverse Event Grading Scale**

Laboratory	Mild (Grade 1)	Moderate (Grade 2)	Severe (Grade 3)
Sodium, low, mEq/L	132 – 135	130 – 131	<130
Sodium, high, mEq/L	146 – 147	148 – 149	150 or greater
Potassium, high, mEq/L	5.2 – 5.3	5.4 – 5.5	>5.5
Potassium, low, mEq/L	3.3 – 3.4	3.1 – 3.2	<3.1
Creatinine, high mg/dL (female)	1.0 - 1.1	1.2 – 2.0	>2
Creatinine, high mg/dL (male)	1.2 - 1.3	1.4 – 2.0	>2
Liver Function Tests (ALT) increase by factor	>1.0-2.5 x ULN	>2.5-5.0 x ULN	>5.0 x ULN
Total bilirubin	>1.0-1.5 x ULN	>1.5-2.0 x ULN	>2.0 x ULN
Hgb (female), low g/dL	10.9 - 11.6	9.4 - 10.8	≤9.3
Hgb (male), low g/dL	13.1 - 13.2	12.5 - 13.0	≤12.4
WBC, increase, cells, $\times 10^3$ u/L	>11.1 - ≤15.0	>15 - ≤20	>20.0
WBC, decrease, cells, $\times 10^3$ u/L	2.5 - <4.4	1.5 - <2.5	<1.5
ANC, $\times 10^3$ u/L	1.2 - <1.7	0.9 - <1.2	<0.9
Platelets, decrease, cells/mm 	124,000-<134,000	100,000<124,000	<100,000
Urine protein	Trace	1+	2+

Note: ULN is the upper limit of the normal range.

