## 14.3 Safety Data

### 14.3.1 Displays of Adverse Events

**Table 30: Overall Summary of Adverse Events**

*[Implementation Note: For the severity rows, a participant will only be counted in one severity category and will be categorized by the maximum severity experienced.]*

	1 µg CJCV2 (N=X)		1 µg CJCV2+ALFQ (N=X)		3 µg CJCV2 (N=X)		3 µg CJCV2+ALFQ (N=X)		10 µg CJCV2 (N=X)		10 µg CJCV2+ALFQ (N=X)		All Participants (N=X)	
Participants with	n	%	n	%	n	%	n	%	n	%	n	%	n	%
At least one local solicited adverse event a	x	x	x	x	x	x	x	x	x	x	x	x	x	x
At least one systemic solicited adverse event a	x	x	x	x	x	x	x	x	x	x	x	x	x	x
At least one unsolicited adverse event b	x	x	x	x	x	x	x	x	x	x	x	x	x	x
Mild (Grade 1)	x	x	x	x	x	x	x	x	x	x	x	x	x	x
Moderate (Grade 2)	x	x	x	x	x	x	x	x	x	x	x	x	x	x
Severe (Grade 3)	x	x	x	x	x	x	x	x	x	x	x	x	x	x
At least one related unsolicited adverse event b	x	x	x	x	x	x	x	x	x	x	x	x	x	x
Mild (Grade 1)	x	x	x	x	x	x	x	x	x	x	x	x	x	x
Moderate (Grade 2)	x	x	x	x	x	x	x	x	x	x	x	x	x	x
Severe (Grade 3)	x	x	x	x	x	x	x	x	x	x	x	x	x	x
At least one clinical laboratory adverse event a	x	x	x	x	x	x	x	x	x	x	x	x	x	x
At least one related clinical laboratory adverse event a	x	x	x	x	x	x	x	x	x	x	x	x	x	x
At least one serious adverse event c,d	x	x	x	x	x	x	x	x	x	x	x	x	x	x

	1 µg CJCV2 (N=X)		1 µg CJCV2+ALFQ (N=X)		3 µg CJCV2 (N=X)		3 µg CJCV2+ALFQ (N=X)		10 µg CJCV2 (N=X)		10 µg CJCV2+ALFQ (N=X)		All Participants (N=X)	
Participants with	n	%	n	%	n	%	n	%	n	%	n	%	n	%
At least one related, serious adverse event c,d	x	x	x	x	x	x	x	x	x	x	x	x	x	x
At least one adverse event leading to early termination e	x	x	x	x	x	x	x	x	x	x	x	x	x	x
At least one medically attended adverse event d	x	x	x	x	x	x	x	x	x	x	x	x	x	x
At least one new onset chronic medical condition d	x	x	x	x	x	x	x	x	x	x	x	x	x	x
At least one potentially immune mediated medical condition d	x	x	x	x	x	x	x	x	x	x	x	x	x	x

Notes: N = Number of participants in the Safety Population.

Participants can only be counted once for each category regardless of the number of events and are categorized by maximum severity.

a Collected from vaccination through 7 days post vaccination for each vaccination.

b Collected from vaccination through 28 days post vaccination for each vaccination.

c A listing of Serious Adverse Events is included in Section 14.3.2.

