d Collected from the time of first vaccination through 12 months following final vaccination.

e As reported on the Adverse Event eCRF.

**Table 31: Non-Serious Adverse Events Occurring in At Least 5% of Participants in Any Treatment Group and All Serious Adverse Events by MedDRA System Organ Class and Preferred Term and Treatment Group**

*[Implementation Note: This table is used to complete the “Other Adverse Event Template” for clinicaltrials.gov reporting. Solicited AEs, unsolicited AEs, and laboratory AEs should be considered for inclusion in this table. Solicited and unsolicited AEs will be considered separately when determining whether the AE meets the 5% criterion and will be reported in separate rows. Solicited AEs (reported on the Treatment Administration Record, Solicited Events Record, or Vital Signs [only temperature within solicited event reporting period] forms) and protocol-defined laboratory parameters (reported on the Local Laboratory Results form) will be included in the systematic collection rows. Any non-serious AEs reported on the Adverse Event form (including graded vital signs and non-protocol defined laboratory parameters) will be included in the non-systematic collection rows. All SAEs should be included in the table, i.e., the 5% criterion does not need to be met for the event to be included in the table. For SAEs and non-serious AEs that were non-systematically collected, an event is defined by each eCRF submitted. For AEs that were systematically collected, an event is defined by occurrence after a single vaccination, i.e., a single participant who received all three vaccinations could contribute up to three events for each symptom/parameter collected. Sort the SOCs by descending incidence (n) and frequency (Events) across all participants (any other ties should be in alphabetical order). Within an SOC, sort the PTs by descending incidence (n) and frequency (Events) across all participants (any other ties should be in alphabetical order).]*

Preferred Term	MedDRA System Organ Class	1 µg CJC2 (N=X)			1 µg CJC2+ALFQ (N=X)			3 µg CJC2 (N=X)			3 µg CJC2+ALFQ (N=X)			10 µg CJC2 (N=X)			10 µg CJC2+ALFQ (N=X)			All Participants (N=X)				
		n	%	Events	n	%	Events	n	%	Events	n	%	Events	n	%	Events	n	%	Events	n	%	Events	n	%
Serious Adverse Events a																								
All	All	x	x	x	x	x	x	x	x	x	x	x	x	x	x	x	x	x	x	x	x	x	x	x
[PT 1]	[SOC 1]	x	x	x	x	x	x	x	x	x	x	x	x	x	x	x	x	x	x	x	x	x	x	x

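### Graded pulse and blood-pressure readings count as unsolicited AEs, but Cohort 1 (1 µg) had 12 scheduled vital-sign days in the AE window against at least 6 in Cohorts 2-3, so its all-causality rates in Tables 30-31 are expected to run higher for a non-vaccine reason

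*SAP*

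**What the plan says.** SAP 4.5.1 (Vital Signs) states that graded vital signs that "represent a worsening condition from baseline are reported as an unsolicited AE with the exception of temperatures" taken within 7 days of a dose, which count as solicited. The note to SAP Table 6 gives the same rule: "Vital signs measurements that meet these grading criteria and represent a worsening of condition from baseline are reported as unsolicited adverse events".

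SAP 4.5.1 (Adverse Events) sets the window: "Unsolicited adverse events will be collected starting after the first vaccination through 28 Days after the last vaccination".

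SAP 9.7 gives the schedule common to all cohorts: "Vital signs will be assessed at screening (Day -30 to -2), Day 1, Day 8, Day 29, Day 36, Day 57", then Days 64, 85 and 113. For Cohort 1, followed under protocol v4.0, it adds that the protocol also "required collection of vital signs at Day 3, Day 15, Day 31, Day 43, Day 59, and Day 71". For Cohorts 2 and 3, "vital signs were only collected on these days if indicated".

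Table 30 has a row headed "At least one unsolicited adverse event", with the six dose-by-ALFQ groups as adjacent columns. The implementation note to Table 31 puts into its non-systematic rows: "Any non-serious AEs reported on the Adverse Event form (including graded vital signs and non-protocol defined laboratory parameters", and says that the table is used for registry reporting. The schedule difference is described in SAP 9.7 and footnoted on the vital-sign tables. SAP 9.3 and Tables 30-31 do not mention it.

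**The concern.** A reading can become an AE only if it is taken. In Cohort 1 pulse and blood pressure were scheduled on twice as many days as in the other cohorts, and cohort and dose are the same thing here. The same background variability therefore has more chances to produce an unsolicited AE at 1 µg than at 3 or 10 µg.

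The primary objective is the safety of three doses, and Tables 30-31 are where a reader will compare them. An artificially higher rate at the lowest dose could hide a rise with dose or make 1 µg look the least well tolerated. The SAP recognises the schedule change where vital signs are tabulated, but not where the AEs from those readings are counted. Correcting the vital-sign tables would leave the AE tables as they are.

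**Working it through.** **The plan's own figure.** The only precision figure for AE rates is the exact 95% interval for 0 events in 10 (SAP section 5). Its upper limit is 1 − 0.025^(1/10) = 0.308, which reproduces the stated 0-31%.

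**Counting days.** The window runs from dose 1 (Day 1) to 28 days after dose 3, Day 57 + 28 = Day 85. Day 1 is baseline and Day 113 lies outside the window.
- Cohort 1: Days 3, 8, 15, 29, 31, 36, 43, 57, 59, 64, 71, 85 = 12.
- Cohorts 2-3: Days 8, 29, 36, 57, 64, 85 = 6 scheduled. This is a minimum, because indicated readings may add to it.
- The Day 85 visit has a ±2-day window. If it falls after the AE window closes, the counts are 11 and 5.

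**Does the worsening condition filter much?** Protocol 4.1.1 admits pulse 50-100, systolic 90-140 and diastolic 55-90. Grade 1 in SAP Table 6 starts one unit outside each limit. A participant within those limits on Day 1 has an ungraded baseline, so any later graded pulse or blood-pressure reading is a worsening.

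**Chance of at least one vital-sign AE with no vaccine effect.** For k days with per-day probability p, independent days: P = 1 − (1 − p)^k. The documents do not give p; the values below are assumptions.

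| p | 12 days | 6 days | Gap (points) |
|---|---|---|---|
| 2% | 21.5% | 11.4% | 10.1 |
| 5% | 46.0% | 26.5% | 19.5 |
| 10% | 71.8% | 46.9% | 24.9 |

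**Allowing for within-person correlation.** Two calculations, both on assumed inputs:
- Simulated systolic, diastolic and pulse readings with means 120/75/72, between-person SD 9/6/8, within-person SD 60%, 80% or 100% of 8/6/7, eligibility limits applied at screening and Day 1, and Table 6 cut-offs. Results, 12 versus 6 days: 14% vs 9%, 28% vs 19%, 47% vs 32%. The gaps are about 5, 10 and 16 points.
- Beta-binomial with the same p as the table. At correlation 0.3: 9.0% vs 6.6%, 21.2% vs 15.7%, 38.3% vs 29.4%. At 0.5 the ratio of 12-day to 6-day chance is 1.22 to 1.26, against 1.53 to 1.89 with independent days.

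**Dilution in the any-unsolicited-AE row.** If a proportion q already has another unsolicited AE, the row shows q + (1 − q)P, so the gap shrinks by the factor 1 − q. With q = 50% (assumed) and p = 2%, independent days: 60.8% vs 55.7%. The simulated gaps of 5, 10 and 16 points become about 2.5, 5 and 8, each less than one participant in a group of 10.

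**Which displays are affected.** Tables 30 and 31 set doses side by side and count all causes. The related rows and Figures 44-51 count only events judged related. Each of Tables 47-61 covers one cohort, so both of its columns share one schedule.

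**The case against.** Several objections carry weight.

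*The primary endpoint is narrower.* A reader might infer that a primary endpoint is inflated. Protocol 2.3 and SAP 3.2 define that endpoint as vaccine-related unsolicited AEs, and Table 30 gives related events their own rows. Chance readings at routine visits are less likely to be judged related. The concern therefore rests mainly on the all-causality rows.

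*Tables 47-61.* A reader might also think these distorted. They are not, since each compares ALFQ with no ALFQ within one cohort.

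*Direction and size.* That 1 µg rates are inflated is an expectation at equal true rates, and the documents cannot show it as a fact. Cohorts were enrolled in sequence under different eligibility rules (BMI below 36, then below 40; travel and family-history exclusions relaxed), and a higher BMI limit could move blood pressure the other way. Actual readings per cohort are unknown.

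*The Table 31 cut.* With 10 per group, one event is 10% and passes the 5% threshold in any arm. Cohort 1 only has more chances to get there.

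*Descriptive, small and disclosed.* No dose test is planned, and the schedule change is stated in SAP 9.7. But the Fisher tests removed in SAP section 15 compared ALFQ groups within a dose, so descriptive tables are the only dose comparison, and wide intervals do not excuse a known imbalance that can be shown cheaply.

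*Excluding readings can mislead too.* Under SAP 9.7, readings on the six days in Cohorts 2-3 were taken only when indicated. Dropping them would delete clinically triggered events at 3 and 10 µg. Days 3, 31 and 59 are two days after a dose, close to the 24-36 hour systemic response described for ALFQ in protocol 3.1.2. This stands, and it rules out a common-schedule table as the sole basis for dose statements.

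**Conclusion.** The concern holds for the all-causality unsolicited-AE rates compared across doses in Tables 30-31. Scheduled opportunities are 12 in Cohort 1 against a minimum of 6 in Cohorts 2-3, and nothing in those tables restricts, separates or footnotes the resulting AEs. At equal true rates the 1 µg columns are expected to be higher for any non-zero chance rate, unless readings are perfectly correlated within a person or indicated readings in Cohorts 2-3 make up the difference.

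The size rests wholly on assumed per-day rates and correlation. For any vital-sign AE, plausible gaps run from a few points to about 25, and they are smaller in the any-unsolicited-AE row. Vaccine-related rows and Figures 44-51 are affected less. The randomised ALFQ contrasts within a cohort are unaffected. The documents do not support saying that the primary endpoint is compromised or that the 1 µg rates are in fact inflated. This is a low-cost improvement to reporting.

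**What to change.** - **Table 30:** keep the all-events rows and add a row for vital-sign AEs, separate from other unsolicited AEs.
- **Tables 30-31:** add a common-schedule sensitivity version. Leave out AEs that arise only from routine scheduled readings on Days 3, 15, 31, 43, 59 and 71. Identify and show any AE from a clinically indicated reading on those days.
- **Footnote on Tables 30-31:** 12 scheduled vital-sign days in Cohort 1, at least 6 in Cohorts 2-3.
- **SAP 9.3.2:** state that comparisons of unsolicited AEs across doses are read from both versions. Neither is free of bias alone, because in Cohort 1 one cannot tell which routine readings would have been taken on clinical grounds.
- **Reconcile the protocol:** section 5.3.1 still lists vital signs, as applicable, at the visits 3 and 15 days after each vaccine. Appendix A does not mark them, and SAP 9.7 says they were taken only if indicated in Cohorts 2-3.

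Tables 47-61 need no change.

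The cost is SAP wording, a few rows and one derived flag. Listing 11 shows no source or visit field, so the flag means matching each AE to the Vital Signs eCRF visit. No new data are needed. Events seen only at routine readings on the extra days leave the sensitivity version but stay in the all-events rows and in Listings 11 and 14.
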